6.5 Exploratory Objective(s)

- To evaluate the T cell function induced by UB-612 vaccine
- To evaluate the safety and immunogenicity of the UB-612 vaccine in adolescents

-
- To evaluate the efficacy of UB-612 vaccine
 - To describe the serological responses to the UB-612 vaccine in confirmed and/or severe COVID-19 cases
 - **To evaluate antibody against SARS-CoV-2 antigens**
 -

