6.6 Exploratory endpoint(s)

- T cell responses to UB-612 measured by ELISpot and flow cytometric assays on Day 57
- **T cell responses to UB-612 measured by ELISpot and flow cytometric assays on 14 days post 3rd dose of UB-612**
- **Geometric mean titer (GMT) of SARS-CoV-2 neutralizing antibody on 14 days post 3rd dose of UB-612**
- **Geometric mean titer (GMT) of antigen-specific antibody (Anti-S1-RBD) 14 days post 3rd dose of UB-612**
- **Geometric mean fold increase in SARS-CoV-2 neutralizing antibody and antigen-specific antibody (Anti-S1-RBD) on 14 days post 3rd dose against pre-3rd dose baseline**
- **Geometric mean titer (GMT) of SARS-CoV-2 neutralizing antibody and antigen-specific antibody (Anti-S1-RBD) on Day 57, Day 197 and Day 365 in adolescents**
- **Seroconversion rate (SCR) of SARS-CoV-2 neutralizing antibody and antigen-specific antibody (Anti-S1-RBD) on Day 57 in adolescents**
- **Geometric mean fold increase in SARS-CoV-2 neutralizing antibody and antigen-specific antibody (Anti-S1-RBD) on Day 57, Day 197, and Day 365 in adolescents**
- Local reactions for up to 7 days following each dose in adolescents
- Systemic events for up to 7 days following each dose in adolescents
- Unsolicited AEs from Day 1 to Day 57 in adolescents
- MAAEs and SAEs from Day 1 to Day **365** in adolescents
- AESIs and ADEs from Day 1 to Day **365** in adolescents
- Changes of safety laboratory measures in adolescents
- COVID-19 incidence per 1000 person-years of follow-up based on PCR test
- To describe the anti-S1-RBD IgG levels and SARS-CoV-2 neutralizing titers to UB-612 in confirmed and/or severe COVID-19 cases
- **To detect antibody against SARS-CoV-2 antigens derived from S2, N, and M protein**

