All subjects will come back on Day 197, Visit 5, for immunogenicity persistence check in immunogenicity group and safety check for safety group. **Once subject completes Visit 5, he or she will be unblinded. Subjects received placebo will withdraw from the study and subjects who received UB-612 vaccine will be invited to join the extension study to determine the durability of the immune response and long-term safety after unblinding. Meanwhile, subjects in vaccine group will be encouraged to have a third dose of UB-612. All subjects who received UB-612 vaccine will be followed up for 12 months.**

All subjects will receive safety calls on Day 8, Day 15, Day 22, Day 36, Day 43, Day 64, Day 71, Day 78, Day 85, Day 253, and Day 309 that will serve both to monitor for unsolicited AEs or/and to monitor for symptoms of COVID-19. After Day 57, each week (i.e., every 7 days) the subject will receive a prompt on their smartphone device to regularly surveillance for signs and symptoms of COVID-19 and SAE. **Subjects who received 3rd dose of UB-612 will receive an extra safety call on 7 days post 3rd vaccination.**

If a Grade 3 local reaction, systemic event, or fever are reported in the reactogenicity e-diary, a telephone contact should occur to ascertain further details and determine whether a site visit is clinically indicated. If suspected Grade 4 local reaction systemic event and /or fever is reported in the reactogenicity e-diary, a site visit should occur to confirm whether the event meets the criteria for Grade 4. All subjects were encouraged to contact site staff once they encountered Grade 3/4 AE. Allergic skin reaction should be monitored for 14 days post vaccination and should be contacted regardless of severity.

If a subject experiences a febrile illness associated with respiratory symptoms, he or she is instructed to contact the site immediately. Subjects may utilize a COVID-19 illness e-diary to prompt him/her to report any symptoms.

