There are two interim reports for EUA application. The first is for safety follow up in core group, and the second is for lot-to-lot consistency. Also, an additional interim report of immunogenicity and safety in adolescents, will be submitted for indication extension.

The surveillance for COVID-19 will be conducted as part of the study. The serological evidences in case of confirmed and/or severe COVID-19 will be described for the change of antibody level in vaccinated subjects. All subjects would be included in the exploratory objectives of protective efficacy against COVID-19 if case detected.

Unblinding will be carried out when the subject in core group or supplementary group has completed Visit 5. Subjects who receive the placebo vaccine will allow to withdraw from the study.

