8.1.8 Visit 5 (Day 197 ± 15 days) –Unblinding / Early Termination

- (1) Conduct physical examination.
- (2) Measure vital signs.

- (3) If subject encountered \geq Grade 3 hypertension, subject should be checked the existence or deterioration of proteinuria or other renal damage sign.

(4) Unblinding

(5) Withdraw subjects who received placebo

- (6) Collect blood sample for following tests only for subjects in lot-to-lot consistency /immunogenicity group:
- Immune response assessments
- (7) Review concomitant medications.
- (8) Record and report adverse event, serious adverse event, or any symptoms of COVID-19 if any has occurred since the previous visit.

The subject will receive a prompt on their smartphone device to regularly surveillance for signs and symptoms of COVID-19 each week.

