COVID-19 incidence per 1000 person-years of follow-up based on PCR test will be descriptively summarized by counts, percentages, and associated Clopper-Pearson 95% CIs for each study group.

- To describe the anti-S1-RBD IgG levels and SARS-CoV-2 neutralizing titers to UB-612 in confirmed and/or severe COVID-19 cases

The anti-S1-RBD IgG levels and SARS-CoV-2 neutralizing titers to UB-612 in confirmed COVID-19 cases will be presented by descriptive summary statistics and associated 95% CIs for each study group.

- **To detect antibody against SARS-CoV-2 antigens derived from S2, N, and M protein**

The results of UBI SARS-CoV-2 ELISA will be presented by descriptive summary statistics

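### V-205 section 10.7 summarizes a per-person-years COVID-19 rate with percentages and Clopper-Pearson intervals, although planned follow-up is about 1.85 times longer on vaccine than on placebo

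*Supplement*

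**What the plan says.** V-205 lists among its exploratory objectives "To evaluate the efficacy of UB-612 vaccine" (section 6.5). The matching endpoint in section 6.6 is "COVID-19 incidence per 1000 person-years of follow-up based on PCR test". Section 10.7 then gives the analysis: "person-years of follow-up based on PCR test will be descriptively summarized by counts, percentages, and associated Clopper-Pearson 95% CIs for each study group". It gives no person-time interval, and no ratio, difference or test between arms.

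Planned follow-up differs by arm. Visit 5 falls on Day 197 with a window of 15 days either side, and its procedures include "Withdraw subjects who received placebo" (section 8.1.8). Section 7.1 agrees: "Subjects received placebo will withdraw from the study". Section 7.3 is softer: "Subjects who receive the placebo vaccine will allow to withdraw from the study". Vaccine recipients are followed for 12 months (section 7.1). The schedule in section 7.2 keeps COVID-19 surveillance running to Day 365, and section 8.1.13 sets a window of 45 days either side of that day. From Day 197 to Day 242 vaccine recipients may also take a third dose.

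Section 10.1 leaves full analysis detail to an SAP. No V-205 SAP is in the supplement.

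**The concern.** The endpoint is cases over time at risk. The summary prescribed for it is cases over subjects, with a binomial interval. With equal follow-up in the two arms, this would be little more than a labelling fault. Here the vaccine arm is watched for nearly twice as long as placebo, so the percentage of subjects infected rises with observation time in one arm only.

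This is the only analysis specified for the stated efficacy objective. Section 7.3 brings all subjects into that objective if cases are detected, and section 9.6 asks the IDMC to evaluate efficacy. Percentages printed by arm will be compared by readers even without a formal test. On that comparison an inert vaccine would look harmful, and a moderately effective one would look useless.

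**Working it through.** The plan gives no attack rate, case target or power for this endpoint, so there is no stated figure to reproduce. The incidence rates below are assumptions.

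**Inputs from V-205.** Placebo exit at Day 197 ± 15 and last vaccine-arm contact at Day 365 ± 45. Core group of about 3850 randomized 6:1 (section 7.4.6), which is 3300 vaccine and 550 placebo.

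**Step 1: follow-up ratio R, vaccine to placebo.**
- Day numbers as planned: 365/197 = 1.85. Counted from Day 1: 364/196 = 1.86.
- Extremes of the windows: 319/211 = 1.51 and 409/181 = 2.26.
- Counting cases from Day 57: 308/140 = 2.20.

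**Step 2: efficacy suggested by whole-study percentages.** With a constant hazard and rare events, apparent efficacy = 1 − (1 − VE) × R.

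| True VE | R = 1.85 | R = 1.51 | R = 2.26 |
|---|---|---|---|
| 0% | −85% | −51% | −126% |
| 50% | 7% | 24% | −13% |

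At R = 1.85, a true efficacy of 1 − 1/1.85 = 46% would read as zero. Without the rare-event approximation, risk = 1 − exp(−rate × time). For assumed rates of 1 to 100 per 1000 person-years, a true 0% then reads as −86% to −82%.

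**Step 3: an example with no vaccine effect.** Assume 20 per 1000 person-years in both arms, counted from Day 1. Expected cases, rounded, are 65 on vaccine and 6 on placebo. Person-years are 3300 × 364/365.25 = 3288.7 and 550 × 196/365.25 = 295.1.

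| Summary | Vaccine | Placebo |
|---|---|---|
| Percentage (Clopper-Pearson), as written | 65/3300 = 1.97% (1.52 to 2.50) | 6/550 = 1.09% (0.40 to 2.36) |
| Rate per 1000 person-years (exact Poisson) | 19.8 (15.3 to 25.2) | 20.3 (7.5 to 44.2) |
| Percentage, both arms cut at Day 197 | 35/3300 = 1.06% | 6/550 = 1.09% |

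Either a person-time denominator or a common cut-off removes the distortion under this model.

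**Step 4: does the interval type matter by itself?** Dividing the Clopper-Pearson limits by mean follow-up (364/365.25 and 196/365.25 years) gives 15.3 to 25.1 on vaccine and 7.5 to 44.0 on placebo, per 1000 person-years. These are almost the Poisson limits in the table. The damage comes from ignoring unequal follow-up, not from using a binomial interval.

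**The case against.** A reader might infer that the trial's efficacy result will be wrong. The documents do not support that. Section 10.7 calls the summary descriptive and plans no efficacy estimate. Where V-205 wants arms compared it says so, for example with Fisher's exact test in sections 10.5.1 and 10.6.1. The analysis sentence still names a rate per 1000 person-years, so it can be read as a rate with counts and percentages alongside. Such a rate carries no bias of this kind under a constant hazard. All of this stands, and it makes the figures in step 2 conditional on whole-study percentages being compared.

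A reader might also infer that vaccine time after Day 197 falls in months with no placebo subject at risk. That is not shown either. Unblinding is subject by subject and enrolment is staggered, with adolescents starting after the core group is complete (section 7.1). Some calendar overlap is therefore possible, and no enrolment dates are given.

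The softer wording in section 7.3 could mean that some placebo recipients stay on, which would narrow the gap. Sections 7.1 and 8.1.8 point the other way, and section 7.5.2.1 gives placebo recipients no third vaccination. The passages should be reconciled.

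Finally, a cut-off or censoring rule could properly sit in the SAP, so its absence here is not a fault. But section 10.7 is not silent. It names a method that does not fit the endpoint, and a correct SAP would have to depart from it.

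**Conclusion.** The sentence in section 10.7 is wrong as written: its statistics do not estimate the rate it names, and no interval for that rate is given. If whole-study percentages are compared, the bias runs against the vaccine by a factor of about 1.85, or 1.51 to 2.26 across the visit windows. This rests on planned visit days, placebo withdrawal at Visit 5, a constant hazard and rare events.

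The point should be fixed, but its reach is limited. The endpoint is exploratory, no sample size rests on it, it is absent from the endpoints listed for the first four interim analyses (section 10.9), and no primary or secondary conclusion changes.

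**What to change.** Replace the sentence in section 10.7 so that each arm has PCR-confirmed cases, person-years at risk and an exact Poisson 95% interval for the rate. State when counting starts and what ends a subject's time at risk.

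Limit any vaccine-placebo contrast to the blinded period, ending at each subject's Visit 5. Person-time alone would not remove changes in incidence over calendar time, or third-dose effects, after that visit. Report vaccine-arm incidence after Visit 5 separately, split by two or three doses received, and do not set it against placebo.

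The change needs only wording and a derivation from dates already collected. Its price is fewer vaccine-arm cases in the contrast: 35 instead of 65 in the example, with the 6 placebo cases unchanged. Because the placebo count dominates precision, the approximate standard error of the log rate ratio rises only from √(1/65 + 1/6) = 0.43 to √(1/35 + 1/6) = 0.44.

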10.8 Subgroup Analysis

Additional study populations and subgroups will be assessed, with further information available in the SAP.

10.9 Interim Analysis

Six interim analyses and reports will be performed when (1) adult immunogenicity data (350 evaluable young adults and 154 evaluable elderly subjects) for Day 57 are available; (2) at least half of core group subjects (at least 3500 evaluable subjects) will be completed Day 85 safety follow up, as EUA application dossier; (3) all immunogenicity data for lot-to lot consistency of Day 57 are available, EUA application dossier; (4) 350 evaluable adolescents completed Day 57 safety follow up, as supplementary dossier for EUA; **(5) immunogenicity and safety data for young and elderly adult subjects receiving 3rd vaccination completed Visit 7, which is 14 days after 3rd vaccination; (6) immunogenicity and safety data for adolescent subjects receiving 3rd vaccination completed Visit 7, which is 14 days after 3rd vaccination.**

The first four analyses and reports will be analysed and drafted by the unblinded statistician, reviewed by the IDMC, and submitted to appropriate regulatory authorities for review if as EUA application dossier or supplementary dossier for EUA.

For the evaluation of safety, immunogenicity, and lot-to-lot consistency, the following endpoints will be included in the first four interim analyses.

- Local reactions, systemic events, unsolicited AEs, and SAEs
- Changes of safety laboratory measures
- Changes of vital signs and physical examinations
- Seroconversion rate of SARS-CoV-2 neutralizing antibody and antigen-specific antibody (Anti-S1-RBD) on Day 57
- Geometric mean titer of SARS-CoV-2 neutralizing antibody and antigen-specific antibody (Anti-S1-RBD) on Day 57
- Geometric mean fold increase in SARS-CoV-2 neutralizing antibody and antigen-specific antibody (Anti-S1-RBD) on Day 57
- Lot consistency by the comparisons of the GMT of SARS-CoV-2 neutralizing titers on Day 57 induced by 3 independent UB-612 vaccine clinical materials. The 95% confidence intervals between groups will be within the margin of 0.5 to 2.

For last two interim analyses (i.e., interim analysis (5) and (6)), the analyses demonstrate the immunogenicity and safety data on the adult and adolescent subjects received 3rd dose of UB-612 including (but not limited to) following endpoints.

- **Local reactions, systemic events, unsolicited AEs, and SAEs after 3rd dose of UB-612**
- **Changes of safety laboratory measures**
- **Changes of vital signs and physical examinations pre/post 3rd dose of UB-612**

- **GMT of SARS-CoV-2 neutralizing antibody on 14 days post 3rd dose of UB-612**
- **GMT of antigen-specific antibody (Anti-S1-RBD) on 14 days post 3rd dose of UB-612**
- **GMFIs in SARS-CoV-2 neutralizing antibody and antigen-specific antibody (Anti-S1-RBD) on 14 days post 3rd dose against pre-3rd dose baseline**

10.10 Handling of Missing Data

All available data will be displayed and utilized in data analysis. No imputation will be considered for the missing observations.

10.11 Protocol Deviations

Protocol deviations will be categorized into important and non-important items, and definitions will be illustrated in the protocol deviation handling plan (PDHD). Events that beyond the PDHD will discuss with sponsor to determine the categorization.

11 QUALITY ASSURANCE AND QUALITY CONTROL

11.1 Audit and Inspection

Study centers and study documentation may be subject to Quality Assurance audit during the course of the study by the sponsor or its nominated representative. In addition, inspections may be conducted by regulatory authorities at their discretion.

11.2 Monitoring

Data for each subject will be recorded on an eCRF. Data collection must be completed for each subject who signs an ICF and is administered study agent.

Due to study design, monitoring activities are divided into blinded and unblinded team. Blinded team will follow the Blinded Monitoring Plan, while unblinded team should follow the Unblinded Monitoring Plan. Unblinded team will report to unblinded UBIA staff. **Members in blinded team should be blinded to immunogenicity data.**

In accordance with current good clinical practice (cGCP) and International Council for Harmonisation (ICH) guidelines, the study monitor will carry out source document verification at regular intervals to ensure that the data collected in the eCRF are accurate and reliable.

The investigator must permit the monitor, the IEC/IRB, the sponsor's internal auditors, and representatives from regulatory authorities direct access to all study-related documents and pertinent hospital or medical records for confirmation of data contained within the eCRFs.

11.3 Data Management and Coding

The sponsor and/or the appointed representative(s) will be responsible for activities associated with the data management of this study. This will include setting up a relevant database and data transfer mechanisms, along with appropriate validation of data and resolution of queries. Data generated within this clinical study will be handled according to the relevant standard operating procedures of the data management and biostatistics departments of the sponsor and/or the appointed representative(s).

Study centers will complete the eCRF. Data entered into the eCRF must be verifiable against source documents at the study center. Data to be recorded directly on the eCRF will be identified and the eCRF will be considered the source document. Any changes to the data entered into the data capture system will be compliant to FDA CFR 21 Part 11.

Medical coding will use Medical Dictionary for Regulatory Activities for AEs.

Missing or inconsistent data will be queried to the investigator for clarification. Subsequent modifications to the database will be documented.

12 RECORDS AND SUPPLIES

12.1 Drug Accountability

On receipt of the study agent (including rescue medication, if relevant), the investigator (or designee) will conduct an inventory of the supplies and verify that study agent supplies are received intact and in the correct amounts before completing a supplies receipt. The investigator will retain a copy of this receipt at the study center and return the original receipt to the study monitor. The monitor may check the study supplies at each study center at any time during the study.

It is the responsibility of the study monitor to ensure that the investigator (or designee) has correctly documented the amount of the study agent received, dispensed, and returned on the dispensing log that will be provided. A full drug accountability log will be maintained at the study center at all times. The study monitor will arrange collection of unused study agent returned by the subject. The study monitor will also perform an inventory of study agent at the close-out visit to the study center. All discrepancies must be accounted for and documented.

12.2 Financing and Insurance

Financing and insurance of this study will be outlined in a separate agreement between the contract research organization and the sponsor.

13 ETHICS

13.1 Independent Ethics Committee or Institutional Review Board

Before initiation of the study at each study center, the protocol, the ICF, other written material given to the subjects, and any other relevant study documentation will be submitted to the appropriate IEC/IRB. Written approval of the study and all relevant study information must be obtained before the study center can be initiated or the study agent is released to the investigator. Any necessary extensions or renewals of IEC/IRB approval must be obtained for changes to the study such as amendments to the protocol, the ICF or other study documentation. The written approval of the IEC/IRB together with the approved ICF must be filed in the study files.

The investigator will report promptly to the IEC/IRB any new information that may adversely affect the safety of the subjects or the conduct of the study. The investigator will submit written summaries of the study status to the IEC/IRB as required. On completion of the study, the IEC/IRB will be notified that the study has ended.

13.2 Regulatory Authorities

Relevant study documentation will be submitted to the regulatory authorities of the participating countries, according to local/national requirements, for review and approval before the beginning of the study. On completion of the study, the regulatory authorities will be notified that the study has ended.

13.3 Ethical Conduct of the Study

The investigator(s) and all parties involved in this study should conduct the study in adherence to the ethical principles based on the Declaration of Helsinki, cGCP, ICH guidelines, and the applicable national and local laws and regulatory requirements.

13.4 Informed Consent

The process of obtaining informed consent must be in accordance with applicable regulatory requirement(s) and must adhere to cGCP.

The investigator is responsible for ensuring that no subject undergoes any study related examination or activity before that subject has given written informed consent to participate in the study.

The investigator or designated personnel will inform the subject of the objectives, methods, anticipated benefits and potential risks and inconveniences of the study. The subject should be given every opportunity to ask for clarification of any points s/he does not understand and, if necessary, ask for more information. At the end of the interview, the subject will be given ample time to consider the study. Subjects will be required to sign and date the ICF. After signatures are obtained, the ICF will be kept and archived by the investigator in the investigator's study file. A signed and dated copy of the subject ICF will be provided to the subject or their authorized representative.

It should be emphasized that the subject may refuse to enter the study or to withdraw from the study at any time, without consequences for their further care or penalty or loss of benefits to which

the subject is otherwise entitled. Subjects who refuse to give or who withdraw written informed consent should not be included or continue in the study.

If new information becomes available that may be relevant to the subject's willingness to continue participation in the study, a new ICF will be approved by the IEC(s)/IRB(s) (and regulatory authorities, if required). The study subjects will be informed about this new information and re-consent will be obtained.

